## 14. Sample Size

Sample size estimates for the clinically relevant outcomes are based on the primary metric: **timely initiation of primary treatment**, a dichotomous outcome (yes/no) calculated for each subject. Since clinical outcomes will be derived from the medical record, we do not anticipate any loss to follow up on these outcomes. We anticipate our study will have 80% power of detecting an advantage to navigation enhanced by a medical-legal partnership, if the enhanced intervention raises the percent in each group receiving timely initiation of care from 76% to 90.5% (testing at the two-tailed .05 level) from patient navigation alone to legal navigation. Comparison of the two study groups on our secondary outcome of time to initiation of cancer treatment, or the number of days to the start of treatment, through survival analysis, takes advantage of more information and should provide somewhat greater power. For example, given the above scenario, (76% vs. 90.5% initiation of care by 90 days) and assuming a constant hazard, (i.e., exponential survival), a log rank test gives 86% power of detecting a difference between the two study groups.

Second, we will conduct separate analyses for the breast and lung cancer participants.

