## Assignment of interventions

### 16. Allocation

- 1) Comparison of study groups on demographic and clinical characteristics will be done to assess the success of randomization. With our stratified blocked randomization scheme, treatment groups will be balanced with regard to gender, insurance (public/private) and race (white/non-white) in a manner proportionate to those in the study population.
- 2) To ensure balanced group assignment on key demographic characteristics, randomization for Breast Cancer patient (females only) will be based on race (white/nonwhite) and insurance status (private/public) resulting in the following strata:
  - a. White, Private insurance
  - b. White, Public insurance
  - c. Nonwhite, Private insurance
  - d. Nonwhite, Public insurance

- 3) If differences in baseline characteristics are detected on other characteristics, these will be included as covariates in later analyses.

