## 17. Blinding

The study statistician conducted the randomization procedure using the statistical software package R version 12.0 [ref]. For each group (a through d above), study participants will be randomized into one of the two treatment groups: patient navigation with legal aid, or standard patient navigation, using a block randomization design to ensure that some balance between treatment groups is achieved as the study progresses. Random block sizes of 2 and 4 will be employed in a random order. Within blocks of size 2, one patient will be randomly assigned to receive patient navigation with legal aid (Intervention) while the other patient will receive patient navigation only (Control). In block sizes of 4, two of the four patients will randomly be assigned to receive patient navigation with legal aid while the other two patients will receive patient navigation only.

The investigator and clinicians assessing the outcomes of the study will remain blinded to each participant's treatment group assignment until the study is completed.

The randomization scheme developed by the Biostatistician will be incorporated into the RedCap data management system. When Screening forms are entered into Redcap, those patients that enroll will be randomized based on their strata and linked to study Ids in RedCap.

Ref: *R Core Team (2012). R: A language and environment for statistical computing. R Foundation for Statistical Computing, Vienna, Austria. ISBN 3-900051-07-0, URL <http://www.R-project.org/>*

Assignment of Study ID- each patient that is eligible and has signed a consent form, will be entered into the RedCAP project for the study, confirming eligibility before the system randomizes participant into the intervention or control group. The patient will be assigned a unique 4 digit study id. The first digit will identify which cancer type the patient has been diagnosed with (1 for Breast, 2 for Lung) and then numbers will be assigned in sequential order.

- Ex: The 5th Breast cancer participant will have Study ID 1005
- Ex: The 29th Lung cancer participant will have Study ID 2029

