### **Analysis**

**Primary Clinical Outcomes: To measure the impact of patient navigation enhanced by MLPB intervention on *receipt of timely and quality cancer care*:**

- Our primary analysis will use multiple logistic regression models to compare the proportion of patients with *timely initiation of treatment* across study groups, adjusting for the influence of race/ethnicity (white vs non-white), cancer site, insurance status (private vs public), and other covariates that may have a significant effect on the outcome and may be unbalanced across the two study groups.
- Study groups will also be compared on the secondary clinical outcome of *time to initiation of primary cancer treatment* (the number of days from diagnosis to start of treatment) through Kaplan-Meier survival curves (unadjusted analyses) and Cox proportional hazards regression models controlling for cancer site and other covariates (adjusted analysis).
- *Receipt of quality care* for each cancer type will be analyzed through logistic regression.
- For the analysis of the rate of missed appointments, patients will differ on the number of scheduled appointments over the study period. We will generate summary measures of the rate and total numbers of missed appointment for the total study cohort and by treatment group.
- The primary analysis will include only participants who have legal issues at baseline (defined by the results of their baseline I-HELP general legal screen, which will take place within one month of new diagnosis). This will be the official sample of patients which the sample size calculations are based (n=117 in each group adjusting for 10% dropout).

**Secondary outcomes: To measure the impact of patient navigation enhanced by MLPB intervention on patient-reported outcomes: *distress, needs, and satisfaction*:**

- Patient-reported outcomes will be measured at baseline, 3 month follow-up, 6 month follow-up, and 12 months using summation scores with established subscales.
- Multiple linear regression models controlling for baseline levels of the outcome (i.e., analysis of covariance models) will be used to compare study groups on changes in *distress* and *psychosocial needs* at follow-up. Multiple linear regression models will also examine intervention effects on *satisfaction* scores.

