- Covariates in each model may include age, race/ethnicity, stage of disease, and other covariates that may have a significant effect on the outcome and may be unbalanced across the two study groups.

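### The Cox and patient-reported-outcome models do not commit to the race and insurance factors used to stratify randomisation, although the primary logistic model does

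*Protocol*

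**What the plan says.** **Randomisation.** Protocol Section 16 states that "randomization for Breast Cancer patient (females only) will be based on race (white/nonwhite) and insurance status (private/public"), which gives four strata. Section 17 adds that within each stratum "Random block sizes of 2 and 4 will be employed in a random order". The four strata are listed for breast cancer patients only, and cancer site is not named as a stratum.

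**Analysis (Section 20).** The randomisation factors are handled differently from model to model:

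- Timely initiation (primary, logistic): race, cancer site and insurance are all named.
- Time to initiation: unadjusted Kaplan-Meier curves, plus "Cox proportional hazards regression models controlling for cancer site and other covariates (adjusted analysis"). Neither race nor insurance is named.
- Quality of care (logistic, for each cancer type): no covariates are named.
- Distress and needs (linear, adjusted for the baseline score) and satisfaction (linear): "Covariates in each model may include age, race/ethnicity, stage of disease, and other covariates that may have a significant effect". The same sentence ties these additions to possible imbalance between the arms as well. Race is optional. Insurance and cancer site are not named.

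Section 16 also promises adjustment where baseline differences appear, but only for characteristics other than those used to stratify.

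**The concern.** Stratified blocking makes the two arms more alike on race and insurance than chance would. An analysis that ignores those factors gets no credit for this. In a linear model, the variance they explain stays in the residual, so the reported standard error exceeds the true sampling error. In a Cox model, omitting a prognostic factor pulls the treatment log hazard ratio toward zero.

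The stated route for adding covariates looks for possible imbalance. Race and insurance are the factors least likely to show it, because the design balances them. The rule also lets the covariate set depend on the observed data.

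The outcomes affected matter. Section 12.1 lists time to initiation and quality of care under primary outcomes, although Sections 14 and 20 call time to initiation secondary. Distress, needs and satisfaction carry the patient-centred aim. What is at stake is some power and a clear prespecified model. False-positive risk is not raised.

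**Working it through.** **1. The plan's own figures.** Section 14 says "We anticipate our study will have 80% power of detecting an advantage" when the enhanced arm moves the percentage "receiving timely initiation of care from 76% to 90.5" per cent, "testing at the two-tailed .05 level". Section 20 gives "n=117 in each group adjusting for 10% dropout".

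n per group = [1.96·√(2·0.8325·0.1675) + 0.8416·√(0.76·0.24 + 0.905·0.095)]² / 0.145² = (1.0351 + 0.4360)² / 0.021025 ≈ 103. Dividing by 0.9 gives 115, close to 117. In reverse, 117 × 0.9 ≈ 105 evaluable per group gives 80.8% power. The stated size therefore reproduces, and 210 patients is a fair analysis set.

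Under a constant hazard, the treatment HR is ln(0.095)/ln(0.24) = 1.649, a log HR of 0.500. With 105 per group, events by day 90 are 105 × (0.76 + 0.905) = 174.8. Schoenfeld power is Φ(√174.8/2 × 0.500 − 1.96) = 91.1%. The protocol states 86% for the log-rank test. That gap is a separate matter and does not affect the comparison below.

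**2. Assumptions the protocol does not supply.** 60% nonwhite; 60% public insurance; the two factors independent; an equal effect g for each factor of 0, 0.2, 0.4 or 0.7. In Cox, g is a log HR, so the factor HRs are about 0.82, 0.67 and 0.50. In linear models, g is in residual SDs.

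**3. Cox model.** 210 patients, blocks of 2 and 4 within the four strata, censoring at day 90, treatment HR 1.649, 1,500 simulated trials per setting:

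| g per factor | log HR without / with | SE without / with | Power without / with | Loss (points) |
|---|---|---|---|---|
| 0 | 0.505 / 0.509 | 0.153 / 0.154 | 91.7 / 91.7% | 0.0 |
| 0.2 | 0.494 / 0.504 | 0.154 / 0.154 | 90.2 / 90.7% | 0.5 |
| 0.4 | 0.485 / 0.513 | 0.154 / 0.155 | 90.2 / 92.1% | 1.9 |
| 0.7 | 0.434 / 0.500 | 0.155 / 0.157 | 81.5 / 89.5% | 8.0 |

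The standard error does not widen when the factors are omitted; the estimate shrinks. With no treatment effect and g = 0.7, the model without the factors rejects 2.7% of the time at a nominal 5%, against 4.7% with them.

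A second setting used a smaller treatment effect (HR 1.5), 365 days of follow-up and 2,000 trials. Power without and with the factors was 81.5 / 82.6%, 79.8 / 83.1% and 77.6 / 83.4% for factor HRs of 0.8, 0.7 and 0.6. The losses are 1.1, 3.3 and 5.8 points. The direction is the same, with somewhat more lost for moderate factors because power starts lower.

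**4. Linear models.** The two factors add variance 2·g²·0.6·0.4 to a residual variance of 1. The reported standard error is therefore inflated by √(1 + 0.48·g²):

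- g = 0.2: √1.0192 = 1.010, about 1%
- g = 0.4: √1.0768 = 1.038, about 4%
- g = 0.7: √1.2352 = 1.111, about 11%

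The simulation agrees: the SE is 0.139, 0.143 and 0.153 without the factors and 0.138 with them. For an assumed treatment effect of 0.35 SD, power without and with them is 70.4 / 71.0%, 69.1 / 71.9% and 64.4 / 71.7%. The losses are 0.6, 2.8 and 7.3 points.

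The same result in terms of R², the share of residual variance explained: the true SE is √(1 − R²) times the reported SE, so the effective critical value is 1.96/√(1 − R²).

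- R² = 5%: critical value 2.011; true test level 4.4%; 80% power becomes Φ(2.802 − 2.011) = 78.5%.
- R² = 10%: critical value 2.066; true test level 3.9%; 80% power becomes Φ(2.802 − 2.066) = 76.9%.

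**The case against.** **The lists are open.** A reader might infer that these models leave race and insurance out. The text does not say so. The Cox model allows unspecified other covariates, race is named as possible for the patient-reported outcomes, and nothing excludes either factor. This objection stands: the defect is a missing commitment.

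**Wide standard errors in Cox.** A reader might carry the linear-model argument over to Cox. The table above shows that this is wrong. The harm there is attenuation and a conservative test.

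**An unadjusted log-rank test.** A reader might infer that one is planned. Section 20 plans Kaplan-Meier curves beside an adjusted Cox model. The log-rank test appears only in the power paragraph of Section 14.

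**The blocks may not be intact.** The primary analysis keeps only patients with a legal need at baseline, which is not a stratum, so balance in that set is only approximate. That weakens the point about the imbalance rule and makes the tests less conservative. It does not remove the power loss. In the limit of no stratification at all, the linear test runs at 5% and power is Φ(2.802·√(1 − R²) − 1.96), or 78.0% at R² = 5% and 75.7% at 10%. The adjusted model is still better.

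**Scope of the strata.** They are documented for breast patients only, and cancer site is not among them. The design argument is clearest for breast cancer. Carrying site over rests on consistency with the primary model.

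**The full list may be in the SAP.** That may be so, and a missing list alone would be no finding. The protocol, however, does state a selection rule, and that rule steers away from the factors used to randomise.

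**Conclusion.** The point holds as a modest, inexpensive improvement. Section 20 fixes race and insurance in the primary model and, without giving a reason, does not fix them in the Cox, quality-of-care or patient-reported models.

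At the protocol's own effect size, omission would cost the Cox analysis about 0 to 2 points of power for per-factor effects up to 0.4, and about 8 points if both reach 0.7. Linear-model standard errors would be about 1% to 11% too wide, costing about 1 to 7 points. No usable prognostic strength is given in the protocol, so these are ranges under assumed strengths and an assumed 60/60 case mix. If the factors are weak, the loss is negligible.

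The errors are conservative, the linear treatment effect is not biased, and the primary logistic analysis is not affected. The documents do not support a claim that the factors are excluded or that a substantial loss of power is certain.

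**What to change.** In Section 20, state that race (white/non-white) and insurance (private/public) are fixed covariates, whatever their observed balance, in the Cox model, the quality-of-care logistic models and every patient-reported-outcome model. Carry over cancer site as in the primary model, except where models are fitted separately by cancer type, since site is then constant. Keep the effect-and-imbalance rule, if wanted, for additional covariates only. If a log-rank test is reported, stratify it by race and insurance; otherwise nothing is needed there.

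The cost is one sentence and two or three degrees of freedom per model. Race and insurance are already recorded in order to randomise, and cancer type is already coded in the study ID.

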## 20. Statistical methods

**Population under study:** Patients newly diagnosed with breast or lung cancer at BMC who volunteer to participate in the study and complete the I-HELP general legal screen at baseline to indicate the presence of legal need.

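### Could the baseline legal-needs screen that defines the primary analysis set have been taken after allocation?

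*Protocol*

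**What the plan says.** Section 20 describes the study population as volunteers who "complete the I-HELP general legal screen at baseline to indicate the presence of legal need". Under Analysis, the primary comparison is limited in the same way: "The primary analysis will include only participants who have legal issues at baseline (defined by the results of their baseline I-HELP general legal screen", with the added timing "which will take place within one month of new diagnosis". The planned size of this set is "n=117 in each group adjusting for 10% dropout", out of 187 randomised per arm (Section 8).

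Section 17 describes randomisation: "When Screening forms are entered into Redcap, those patients that enroll will be randomized based on their strata". The system acts after consent, "confirming eligibility before the system randomizes participant into the intervention or control group". The I-HELP screen is not among the eligibility criteria in Section 10. It is not a stratification factor in Section 16 either: for breast cancer patients, randomisation "will be based on race (white/nonwhite) and insurance status (private/public").

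The table in Section 13 lists I-HELP under Baseline, together with two forms marked for the intervention arm only. Section 11 has the intervention navigator give one of these, the Detailed Legal Screen, in the first week after enrolment.

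On blinding, Section 17 states: "The investigator and clinicians assessing the outcomes of the study will remain blinded". It does not mention the research assistants, who give the study forms according to Section 13.

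**The concern.** A subset defined by a measure taken before randomisation keeps the protection of randomisation. A subset defined by a measure that allocation can influence does not. Here the explicit time limit is counted from diagnosis, allocation as described does not need the I-HELP result, and the Baseline column contains forms that can exist only after allocation. On a strict reading, then, the screen could be given to a patient whose arm is known, and in the intervention arm even after the more detailed legal interview.

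That interview could make a patient more ready to report a legal need, or more likely to complete the screen. The intervention arm's primary set would then hold patients whose counterparts among the controls were left out. Blinded outcome assessment and treatment dates from the chart would not help, because the distortion acts on who is counted and not on how the outcome is measured. The filter is also large: 187 - 117 = 70 patients per arm are expected to fall outside the primary set.

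**Working it through.** **1. The plan's own figure.** Inputs from Section 14: 76% versus 90.5% timely, two-sided 5% level, 80% power. With the pooled two-proportion formula and mean rate 0.8325,

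n = [1.96 × √(2 × 0.8325 × 0.1675) + 0.842 × √(0.76 × 0.24 + 0.905 × 0.095)]² / 0.145² = 102.9, so 103 per arm.

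Allowing for 10% dropout, 103 / 0.9 = 114.4, so 115, close to the stated 117. Read the other way, 117 × 0.9 = 105 analysed per arm gives 80.8% power. The sample size therefore fits a subset defined in advance, and the order of the screen does not alter it.

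**2. The passages side by side.**

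| Question | What the protocol gives |
|---|---|
| When is I-HELP done? | At baseline (Section 20, twice; Section 13 table); within one month of diagnosis (Section 20) |
| When may a patient enrol? | Up to 30 days from diagnosis (Sections 10 and 15) |
| What triggers allocation? | Consent, eligibility check, entry of Screening forms (Section 17) |
| Is I-HELP placed after allocation anywhere? | No |
| Is I-HELP placed before allocation anywhere? | Not in so many words |

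The one-month limit and the enrolment window have the same length and the same starting point. The natural reading is that the limit restates the enrolment window and does not create a separate, later one.

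**3. The latest order the stated limits allow.** For a patient enrolled on day *d* after diagnosis, with the Detailed Legal Screen on the day of enrolment, I-HELP could follow it by up to 30 - *d* days: 30 days for *d* = 0 and 16 for *d* = 14. These are bounds on what is not excluded. They say nothing about usual practice.

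**4. Size if the order did fail.** Everything in this step other than 117, 187, 76% and 10% dropout is assumed. Take the I-HELP-positive share as 117/187 = 0.626 and suppose no true effect. Let a further share *x* of the intervention arm become positive only because of allocation, and let a proportion *q* of these extra patients be timely, with *q* from 0.60 to 0.95. Then

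shift = (0.626 × 0.76 + *x* × *q*) / (0.626 + *x*) - 0.76.

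The false-positive rate is that of the same two-sided test, with 105 controls and 105 × (0.626 + *x*) / 0.626 intervention patients.

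| *x* | Extra patients of 187 | Share of I-HELP-negatives | Shift, *q* = 0.60 to 0.95 (points) | Highest false-positive rate |
|---|---|---|---|---|
| 0.05 | 9 | 13% | -1.2 to +1.4 | 5.7% |
| 0.10 | 19 | 27% | -2.2 to +2.6 | 7.6% |
| 0.15 | 28 | 40% | -3.1 to +3.7 | 10.5% |

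If the extra patients resemble the others (*q* = 0.76), the shift is zero and the rate stays at 5.0% for every *x*. With 117 controls the three highest rates are 5.8%, 7.9% and 11.2%.

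**The case for a change.** The best case for a change is that this protocol uses the word baseline loosely. Its Baseline column includes a form that only patients already allocated to the intervention can receive, so the label alone does not prove that I-HELP came first. Section 18 separates surveys given to participants from screening information completed by staff, so the Screening forms that trigger allocation cannot be assumed to include I-HELP. Section 26 can be read to let baseline surveys follow consent, at a later visit or by telephone. The order of a screen that fixes the primary set is a matter of conduct, and one sentence would settle it.

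Much of this stands: the order is not written down in the available text. But the table shows only that some baseline forms follow allocation, and these are the two marked for one arm; I-HELP is given in both. Section 26 concerns patients who cannot stay to enrol and does not say that they have been randomised. Silence on the research assistants' blinding does not show that they knew the arm when they gave the screen. The consent procedure to which Section 26 refers is not in the text at hand and may state the sequence.

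**Conclusion.** The concern describes an unwritten sequence. It does not show a rule that gives a wrong result. Under the ordinary meaning of baseline, supported by the matching 30-day windows, the I-HELP-positive subset is a proper randomised comparison with about 81% power at 105 analysed per arm.

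The gap is one that analysts fill sensibly. They take I-HELP results dated before allocation as defining the set, and they can compare the two dates in the existing records. An analysis of all randomised patients, or a count by arm of any late screens, is supportive detail of the kind a statistical analysis plan commonly holds, and that plan is not at hand. Recruitment is described in the past tense, so a rule on the order of steps in the database may no longer have any use.

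The possible harm is unproven and could run in either direction. It is near nominal at 5% extra positives (at most 5.7%, or 5.8% with 117 controls). It becomes material only if allocation turned a quarter or more of the intervention arm's I-HELP-negatives positive and those patients differed clearly in timeliness. This conclusion rests on I-HELP having been given around enrolment, as its label says. Dates showing many screens after allocation would reopen the question.
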